## 2.3.SUMMARY OF RELEVANT DATA

A comprehensive panel of nonclinical studies have been conducted to evaluate the efficacy and safety of RMP-A03 to support the initiation of the first-in-human clinical trial. A brief summary of the information from nonclinical studies is presented below.

The pharmacology studies included the kinase inhibition of RMP-A03 at the molecular and cellular level, and the potential therapeutic effects of RMP-A03 on [REDACTED]

The nonclinical pharmacokinetic studies including absorption, distribution, metabolism and drug-drug interaction of RMP-A03 were evaluated in vitro and in preclinical species. [REDACTED]

[REDACTED] Following ocular instillation, the systemic exposure of RMP-A03 was negligible.

The toxicity of RMP-A03 was evaluated in single-dose (iv) and up to 28-day (ocular) repeat-dose GLP-compliant toxicity studies with the maximally formulatable concentration [REDACTED]. Measurable but extremely low systemic exposure was detected after ocular dosing. No test article-related untoward ocular effects or systemic toxicity were observed [REDACTED].

In summary, nonclinical studies performed to date have demonstrated an acceptable safety profile of RMP-A03 to initiate the IND opening clinical trial. Please refer to the Investigator's Brochure for detailed nonclinical study design and results.

## 2.4.RISKS AND BENEFITS TO HUMAN SUBJECTS

RMP-A03 is a new investigational drug and this study is the first-in-human clinical trial of RMP-A03. The risks associated with RPM-A03 are not well understood at this time.

Since there is no approved treatment for pterygium at this time point, if efficacious, RMP-A03 may slow down the progression of pterygium in clinical trial patients.

## 3. STUDY OBJECTIVES

Primary objective(s):

- To assess the safety and tolerability of RMP-A03 (Stage 1 and 2)

Secondary objective(s):

- To evaluate the treatment response to RMP-A03 compared to vehicle as determined by change from baseline in pterygium characteristics.

## 4. INVESTIGATIONAL PLAN

### 4.1. STUDY DESIGN

This is a first-in-human study with a 2-stage design. Only 1 eye per subject will be enrolled into the study (See designation of study eye in Section 4.1.1).

**Stage 1**, is an open-label dose escalation, 7-day study to determine the maximum tolerated dose (MTD) of the 4 evaluated doses of RMP-A03 in healthy volunteers. Four escalating doses of RMP-A03 ocular suspension [REDACTED] will be evaluated in Stage 1, given that no safety concerns are identified with each escalating dose. Up to 5 subjects are planned for enrollment into each dose cohort. The first cohort will begin with the lowest dose of study drug (RMP-A03 ocular suspension [REDACTED]).

At the screening visit, following informed consent, demographic information, relevant medical and ophthalmic history will be recorded. All prescription and over-the-counter medications taken 30 days prior to the screening and during the study will be recorded (diagnostic eye drops do not need to be recorded). Urine pregnancy test must be performed for women of childbearing potential (WOCBP). Screening assessments will include a complete physical examination, heart rate and blood pressure, clinical labs, comprehensive ophthalmic assessments, pterygium assessments, and the ocular comfort questionnaire. At Day 1 baseline visit, after completing all required assessments and confirming eligibility, the study subject will instill a single eye drop of RMP-A03 to the study eye one time at Day 1. The study staff will observe the eye drop instillation. Post-baseline evaluations on Day 1 will include physical examination, heart rate and blood pressure, comprehensive ophthalmic assessments, the ocular comfort questionnaire, and AE collection. Upon confirmation of acceptable tolerability and no immediate safety concerns, study drug will be dispensed at the end of Day 1 and subjects will be instructed to instill 1 drop of study medication in the study eye 3 times daily (TID, at least 3 hours apart), starting from the morning of Day 2 to Day 6. On Day 7, subjects will return to the clinic, and a single eye drop of RMP A03 will be administered in the study eye before completion of the final examinations (see Table 1-1 for study visits and procedures and Figure 1 for the study schematic).

Escalation to the next dose cohort will only occur after the 7-day safety data for all subjects in the preceding cohort has been reviewed by the SC and upon confirmation of no safety concerns.

**Note, intrasubject escalation will not be permitted.**

**Stage 2** will initiate upon completion of Stage 1 and following determination of MTD among the 4 evaluated doses. Stage 2 is a randomized, doubled-masked, placebo-controlled study

comparing the efficacy and safety of RMP-A03 with placebo in patients with pterygium. Approximately 75 patients are planned to be randomized to 1 of 3 treatment groups in a 1:1:1 ratio. These treatment groups will consist of the 2 doses of RMP-A03 and the RMP-A03 vehicle. A single eye drop of RMP-A03 or RMP-A03 vehicle will be applied TID to the study eye for a total of 28 days. Patients will be followed for a total of 84 days. The study will consist of 7 visits as follows: Screening (up to 60 days prior to the baseline visit), Baseline/Day 1, Day 7, Day 14 (Phone Visit), Day 28, Day 56, and Day 84 (see Table 1-2 for study visits and procedures and Figure 1 for the study schematic).

#### **4.1.1. DESIGNATION OF STUDY EYE**

Study eye will be defined as the eye that meets all of the inclusion and none of the exclusion criteria. If both eyes meet criteria, the eye with higher pterygium vascularity grading will be chosen as the study eye. If both eyes have the same pterygium vascularity grading, the right eye (OD) will be determined as the study eye.

#### **4.2.SAFETY COMMITTEE AND STOPPING RULES**

An SC will be assembled to provide assessment of safety data during the study. An essential component of risk management in early phase clinical trials is implementation of stopping rules to ensure the safety of study participants.

Stopping Rules will be considered during the safety review if any of the following events are reported:

- Worsening of BCDVA of  $\geq 3$  lines in the study eye, deemed as related to study drug in  $>2$  subjects
- IOP increase to  $> 27$  mmHg that cannot be controlled by medication, deemed as related to study drug in  $>2$  subjects
- Ocular inflammation  $>$  grade +2, deemed as related to the study drug in  $>2$  subjects
- Corneal edema worsening by  $> 2$  grades, deemed as related to the study drug in  $>2$  subjects
- Any other serious ocular or systemic adverse event that, in the opinion of the Investigators, is related to the study drug in  $> 2$  subjects

All available safety data for the cohort will be reviewed by the SC to evaluate feasibility of further dosing of the study drug, and/or the safety of dose escalation. Recommendations by the SC may result in amendment of the study design or discontinuation of a dose cohort, or the clinical trial.

#### **4.3.SCIENTIFIC RATIONAL FOR STUDY DESIGN**

The small sample size, single-arm, open-label, follow-up period is a common and acceptable study design for first-in-human studies. The sequential dose escalation allows for risk mitigation before exposing additional participants to subtherapeutic doses.

The randomized, doubled-masked, placebo-controlled methodology of the Stage 2 portion of the trial is optimal on clinical trials to reduce bias and provide reliable safety and efficacy information.

Stopping rules are implemented to minimize the risk to study participants.

#### 4.4.DOSING RATIONALE

The clinical doses, treatment period, and dosing regimen were selected based on preclinical data.

██████████ are selected as toxicological species for the GLP ocular toxicity studies of RMP-A03 based on comparable human eye size and anatomical structure. Toxicology studies indicated that no local and systemic toxicity of RMP-A03 were observed after 28-day ocular administrations in ██████████. Following RMP-A03 treatment at ██████████, for 28 continuous days, the NOAEL was defined as ██████████ in both studies. The corresponding systemic exposure of ██████████ ocular instillation was approximately ██████████, which was more than ██████████ lower than the  $C_{max}$  at NOAEL in 28 days iv repeated dosing.

Considering the totality of the nonclinical data, a first-in human (FIH) starting dose of ██████████ proposed. As RMP-A03 did not induce ocular toxicity in ██████████ in the 28-day ocular toxicity studies, nonclinical data support the maximum dose of ██████████.

#### 4.5.RANDOMIZATION

Randomization will be implemented in Stage 2. Consented subjects who meet all enrollment criteria will be randomly assigned to receive 1 of 3 treatments (RMP-A03 Dose 1, RMP-A03 Dose 2 or vehicle) in a 1:1:1 ratio. Randomization schedule will be optimized to achieve a balanced distribution of treatment assignment by baseline ██████████.

#### 4.6.MASKING

In Stage 2, subjects and study personnel, including but not limited to investigators, study staff, central lab, clinical monitors, and designated staff within the Sponsor and the Sponsor's representatives, will remain masked to the study treatment assignments. There will be a small dedicated unmasked team comprised of Sponsor and Sponsor representatives that will manage IP supply, IRT services, and randomization schematics.

If there is a need to unmask the study drug assignment for a subject, the Principal Investigator must notify the Sponsor's Medical Monitor prior to unmasking of the study drug. Refer to Section 10.7 for a description of emergency unmasking procedures.

The reason for unmasking must be documented in the source document for the subject. If a subject's study drug assignment is unmasked, the subject should remain in the study and continue the protocol-specified safety follow-up evaluations.

## **5. SELECTION AND WITHDRAWAL OF SUBJECTS**

### **5.1.INCLUSION CRITERIA OF STAGE 1**

Participants must meet all of the following criteria for enrollment in Stage 1:

1. Must be 18 years of age or older at time of consent
2. Healthy as determined by a physician, based on a medical evaluation including medical history, physical examination, and laboratory tests
3. Best-corrected visual acuity of 20/40 or better (Snellen equivalent) in both eyes
4. Willingness to comply with the study procedures and study drug administration and to return for all study visits

### **5.2.EXCLUSION CRITERIA OF STAGE 1**

Subjects meeting one or more of the following criteria must be excluded from the Stage 1:

Ophthalmic:

1. History or current eye disease other than refractive error, incipient cataract, strabismic amblyopia, or anisometropic amblyopia that might interfere with interpretation of the safety
2. History of ocular surgery within the 3 months prior to screening
3. Use of any ocular medication in either eye within 14 days of screening and throughout the study, with the exception of a) lid scrubs (which may be used prior to, but not after, screening), b) lubricating drops for dry eye (which may be used throughout the study no more than 2 times per day and at least 10 minutes between the study eye drop and the lubricating eye drop)
4. Use of contact lenses in the study eye. Contact lenses wearers must discontinue wearing at least 3 days prior to Day 1 visit and throughout the study
5. Known hypersensitivity to benzalkonium chloride or excipients of RMP-A03 ophthalmic solution
6. Cannot demonstrate proper delivery of the eye drop, or, in the investigator's opinion, unable to deliver the eye drop consistently

Systemic:

7. Clinically significant abnormalities in laboratory tests at screening
8. History or presence of clinically significant cardiovascular, pulmonary, hepatic, renal, hematological, gastrointestinal, endocrine, immunologic, dermatologic (including

sensitive skin on the face), neurological, or psychiatric disease, or any other clinically significant disease not deemed acceptable by the Investigator

9. Use of prescription or non-prescription drugs, including vitamins, herbal and dietary supplements within 7 days prior to the first dose of study medication, unless in the opinion of the Investigator and Medical Monitor the medication will not interfere with the study procedures or compromise subject safety
10. A positive pre-study drug/alcohol screen
11. Participation in any investigational study within 30 days prior to screening
12. Female participants who are pregnant, or females of childbearing potential who are pregnant, nursing, planning a pregnancy, or not using a medically acceptable form of birth control (see Section 5.6). Females of childbearing potential must have a negative pregnancy test at baseline

### 5.3.INCLUSION CRITERIA OF STAGE 2

Participants must meet all of the following criteria for enrollment in Stage 2:

1. Must be 18 years of age or older at time of consent
2. Diagnosis of pterygium with a) pterygium vascularity [REDACTED] per the Investigator's assessment using the slit-lamp and the anterior segment photography confirmed by the Medical Monitor at Screening, b) pterygium size at limbus [REDACTED] as determined by the Investigator under slit-lamp at Screening, c) encroachment onto the cornea [REDACTED] as determined by the Investigator under slit-lamp at Screening and d) T2 (intermediate) or T3 (opaque) as determined by the Investigator under slit-lamp following pterygium morphology grading scale at Screening
3. Best-corrected visual acuity of 20/200 or better (Snellen equivalent) in both eyes
4. Willingness to comply with the study procedures and study drug administration and to return for all study visits

### 5.4.EXCLUSION CRITERIA OF STAGE 2

Subjects meeting one or more of the following criteria must be excluded from the Stage 2:

#### Ophthalmic:

1. Presence of ocular disease in either eye (e.g., pinguecula, corneal abnormalities, active ocular infection or inflammation, glaucoma, retina diseases, history of herpes keratitis, or ocular neoplasia) which might interfere with interpretation of the study efficacy or safety assessments
2. Double pterygium (i.e., nasal and temporal pterygium), pterygium that requires immediate surgery or pseudo-ptyerygium (e.g., chemical or thermal burn, trauma, marginal corneal disease)

3. History of ocular surgery (e.g., corneal transplant, glaucoma surgery, retina surgery) or other ocular surgeries within the 3 months prior to screening with the exception of pterygium surgery
4. Ocular trauma within 6 months prior to screening or non-invasive laser treatment within the 3 months prior to screening
5. Use of any ocular medication in either eye within 14 days of screening and throughout the study, with the exception of a) lid scrubs (which may be used prior to, but not after, screening), b) lubricating drops for dry eye (which may be used throughout the study no more than 2 times per day and at least 10 minutes between the study eye drop and the lubricating eye drop)
6. Use of contact lenses in the study eye. Contact lenses wearers must discontinue wearing at least 3 days prior to Day 1 visit and throughout the study
7. Known hypersensitivity to benzalkonium chloride or excipients of RMP-A03 ophthalmic solution
8. Cannot demonstrate proper delivery of the eye drop, or, in the investigator's opinion, unable to deliver the eye drop consistently

Systemic:

9. Clinically significant abnormalities in laboratory tests at screening
10. Clinically significant systemic disease which may place the participant at risk or confound study results
11. Participation in any investigational study within 30 days prior to screening
12. Female participants who are pregnant, or females of childbearing potential who are pregnant, nursing, planning a pregnancy, or not using a medically acceptable form of birth control (see Section 5.6). Females of childbearing potential must have a negative pregnancy test at baseline

## 5.5. WITHDRAWAL

### 5.5.1. WITHDRAWAL CRITERIA

Subjects may choose to withdraw from the study at any time for any reason. In addition, subjects may be withdrawn from the study by the Investigator for any of the following reasons:

- The subject is unwilling or unable to adhere to the protocol.
- Any SAE, clinically significant AE, severe laboratory abnormality, intercurrent illness, or other medical condition that indicates to the Investigator that continued participation is not in the best interest of the subject.
- Other medical reason, at the discretion of the Investigator and/or the Medical Monitor.

### 5.5.2. WITHDRAWAL PROCEDURES

- If it is necessary for a subject to discontinue the study drug/study earlier than planned, subjects should complete Early Termination procedures (see [Table 1-1](#) and [Table 1-2](#)) and return the study drug, as applicable. Date of last dose should be recorded.
- The Investigator must notify the Sponsor and the Medical Monitor within 24 hours when a subject has been withdrawn from the study. Any subject withdrawn because of a related AE (whether serious or non-serious), including clinically significant abnormal laboratory test values, will be evaluated by the Investigator or a designee and be treated and/or followed until the symptoms resolve or values return to normal or acceptable levels, as judged by the Investigator.
- If a subject does not return for a scheduled visit, every effort should be made to contact the subject. If a subject withdraws from the study, the Investigator or designee should inquire about the reason for withdrawal, and follow-up with the subject by phone as scheduled to collect AE information.
- If the subject withdraws from the study and also withdraws consent for disclosure of future information, no further evaluations will be performed, and no additional data will be collected. The Sponsor may retain and continue to use any data collected before such withdrawal of consent; these data will be included in the safety database.

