**Table 1-2: Schedule of Visits and procedures in Stage 2**

Procedures	Screening Day-60 to -1  (Visit 1)	Baseline Day1  (Visit 2)	Follow-up Day 7±1 day  (Visit 3)	Follow-up Day 14±3 days Phone call  (Visit 4)	Follow-up Day 28±3 days  (Visit 5)	Follow-up Day 56±4 days  (Visit 6)	Follow-up/ Exit  Day 84±5 days  (Visit 7)
Informed Consent	X						
Inclusion/Exclusion	X	X					
Demographics	X						
Medical/Ophthalmic History	X	X	X	X	X	X	X
Concomitant Medications	X	X	X	X	X	X	X
Heart Rate and Blood Pressure	X	X	X		X	X	X
Urine Pregnancy Test 	X	X					X
Clinical Labs	X						X
Adverse Events 		X	X	X	X	X	X
Ocular Comfort Index	X	X	X		X	X	X
BCDVA	X	X	X		X	X	X
Intraocular Pressure	X	X	X		X	X	X
Pterygium Photography	X	SE	SE		SE	SE	SE
Pterygium Assessments	X	SE	SE		SE	SE	SE
Slit Lamp Biomicroscopy	X	X	X		X	X	X
Indirect Ophthalmoscopy	X	X	X		X	X	X
Eye Drop Instillation Evaluation 	X						
Study Drug Administration		X 					
Study Drug Dispensing		X					
Study Drug Accountability					X 		

Abbreviations: SE= Study eye

 Schedule the Telephone visit (Visit 4) on Day 14. Change in medical history or concomitant medications should be assessed by the investigator for AEs. Study drug compliance issues and reeducation of subjects should be documented in the source documents

 Every effort should be made to complete all Exit procedures at Early Termination

Suzhou Raymon Pharmaceuticals

 A negative result on a urine pregnancy test before administration of study drug for women of childbearing potential is required for eligibility

[figure not shown]
 AEs should be assessed before and after administration of study drug

 First dose to be administered by the study subject at Day 1. The study staff will observe the IP instillation

 Collect dispensed kit at Visit 5

[figure not shown]
 Study staff must confirm the subject can demonstrate proper delivery of eye drops prior to advancing to the Baseline/Day 1 visit. It should not be confused with the study staff observation of subjects' first dose of IP performed at the Baseline/Day 1, Visit 2

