### 5.5.3. DOCUMENTATION OF WITHDRAWAL

The reason(s) for withdrawal from the study drug/study must be recorded in the subject's medical record and case report forms (CRF).

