## 10.7. EMERGENCY IDENTIFICATION OF STUDY MEDICATION

In the event of a medical emergency, when knowledge of the subject's treatment assignment may influence the subject's clinical care, the Investigator may obtain the treatment assignment of the subject experiencing the emergency through the unmasked statistician/designee. However, prior to unmasking, the Investigator should make every effort to contact the Medical Monitor.

If unmasking is necessary, the Investigator must document the reasons for unmasking in the subject's source documents but should not divulge the subject's treatment assignment to any individuals except the Medical Monitor (if required) and those individuals involved in the direct care of the subject. The date and the reasons for breaking the mask must be submitted to the Sponsor within 24 hours.

If a subject's treatment assignment is unblinded, the subject should remain in the study and continue the protocol-specified follow-up evaluations.

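### Protocol 5.5.2 and 5.5.3 do not separate stopping study drug from leaving the study, so no eye examination or hyperemia grade is provided for after Early Termination in patients who stop drops early

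*Protocol*

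**What the plan says.** **Stopping.** Protocol 5.5.1 lists reasons for withdrawal from the study and gives no separate list for stopping drug alone. Section 5.5.2 then states: "If it is necessary for a subject to discontinue the study drug/study earlier than planned, subjects should complete Early Termination procedures". The drug is returned and the last dose date recorded. Section 5.5.3 also joins the two events: "The reason(s) for withdrawal from the study drug/study must be recorded".

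**The Early Termination visit.** Table 1-2, footnote 2: "Every effort should be made to complete all Exit procedures at Early Termination". The Exit column (Visit 7) includes BCDVA, IOP, slit lamp, indirect ophthalmoscopy, pterygium photography and assessments, laboratory tests and AEs.

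**Afterwards.** For a subject who withdraws from the study, 5.5.2 tells the site to "follow-up with the subject by phone as scheduled to collect AE information", unless consent for disclosure of future information is also withdrawn. A subject withdrawn for a related AE is "treated and/or followed until the symptoms resolve or values return to normal or acceptable levels, as judged by the Investigator". Protocol 10.5 follows related AEs and all SAEs to resolution or a stable state.

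**Planned follow-up.** Stage 2 treatment lasts 28 days. Protocol 4.1: "Patients will be followed for a total of 84 days".

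**Unmasked patients.** Protocol 10.7 says that "the subject should remain in the study and continue the protocol-specified follow-up evaluations". Protocol 4.6 says that "the subject should remain in the study and continue the protocol-specified safety follow-up evaluations".

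**SAP.** The MMRM uses observed data in the mITT set (7.3.1.1). The mITT ANCOVA uses LOCF (7.3.1.2), which 7.2 permits for Day 7 and Day 28 from scheduled or unscheduled post-baseline visits. Disposition (6.2) counts discontinuation from the study only, while 7.4.1 tabulates TEAEs that lead to discontinuation of study drug.

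**The concern.** Stopping drops and leaving a trial are different events. A patient who stops because of stinging may be quite willing to return for examination. Days 56 and 84 are off drug for every patient, so stopping early is no reason to miss them.

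The primary objective is safety and tolerability in a first-in-human study, and patients who stop for ocular intolerance are among the most informative. A phone call can collect symptoms and events, but it cannot measure visual acuity or pressure or examine the cornea and fundus.

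For efficacy, a Day 28 grade that could have been observed is left to the model or to carry-forward. The sample size leaves no slack: 25 patients treated per arm equals the 25 completers assumed for power, and only Stage 1 subjects may be replaced.

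**Working it through.** **1. Follow the text for a patient who stops on Day 10.** The post-baseline on-site visits are Days 7, 28, 56 and 84. This patient has Day 7 and an Early Termination examination at about Day 10. No section schedules Days 28, 56 or 84, so three of the four on-site visits have no provision. A patient stopping between Day 25 and Day 31 differs, because Early Termination then falls within the Day 28 ± 3 window.

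**2. Safety window.** SAP 7.4.1 closes the TEAE window 30 days after last dose. For the Day 10 stopper that is Day 10 + 30 = Day 40: the Day 28 visit lies inside it, Days 56 and 84 outside. AEs can still be reported by phone. What is lost is examination data, which SAP 7.4.2 summarizes by visit.

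**3. Day 28 grade.** In the MMRM it is missing, though the Day 7 grade still contributes. In the mITT ANCOVA the Early Termination grade can be carried forward. The SAP has no visit-window rule for placing an Early Termination grade and no stated strategy for drug discontinuation.

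**4. The plan's power figure.** Inputs (Protocol 9.5, SAP 9): 25 completers per arm, difference 0.66, SD 0.7, alpha 0.05, two-sided per SAP 7.3. Standard error = 0.7 × √(2/25) = 0.198, and 0.66 / 0.198 = 3.33. Power is 91.5% by normal approximation and 90.4% by t-test (48 df), so the stated 90% reproduces. The 0.10 level in Protocol 9.1 would give 95.4% (normal), so 0.05 is the basis used.

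**5. Assumed stopping rates.** The documents give none. Column A drops the stoppers from both arms being compared. Column B keeps all 25 observed and gives active-arm stoppers zero benefit, so the difference is 0.66 × (1 − d). SD stays at 0.7, which slightly flatters column B. Powers are by t-test.

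| Stopping, d | A: n per arm | A: power | B: difference | B: power | d × 0.66 |
|---|---|---|---|---|---|
| 4% | 24 | 89.2% | 0.634 | 88.0% | 0.026 |
| 8% | 23 | 87.8% | 0.607 | 85.2% | 0.053 |
| 12% | 22 | 86.3% | 0.581 | 82.0% | 0.079 |
| 20% | 20 | 82.8% | 0.528 | 74.3% | 0.132 |

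The last column is how far the difference would be overstated if stoppers had zero benefit, the model credited them with the full 0.66, and no vehicle-arm dropout offset it. It is an upper bound under those assumptions. The MMRM uses a stopper's earlier grades, so a poor Day 7 grade pulls the implied Day 28 value down.

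**The case against.** **No rule says that stopping drug means leaving the study.** True. The phone-contact sentence is conditioned on withdrawal from the study, and SAP 7.4.1 treats drug discontinuation as its own category. A reader might infer an explicit exclusion from later visits; the text does not state one. It is the natural reading of the joint wording, and nothing provides the alternative.

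**The safety and efficacy questions are still answered.** Largely fair. One full examination and grade is planned, AE calls continue, related AEs and all SAEs are followed, and LOCF can supply a Day 28 value. A reader might conclude that 84-day safety and Day 28 efficacy go unanswered for these patients. The documents support less: both are answered by examination up to Early Termination, then by phone, by AE follow-up or by carry-forward.

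**The unmasking rule is not a contradiction.** Agreed. It concerns a broken mask, and 4.6 limits continuation to safety evaluations. It shows only that the protocol can state a stay-in-study rule when it means to.

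**Keeping stoppers does not protect power.** This stands. Under zero benefit, power is 85.2% with them kept against 87.8% with them lost at 8% stopping, and 74.3% against 82.8% at 20%. Analysing off-drug grades as randomized also chooses a treatment-policy question. That bears on how the grades are analysed, not on whether they are collected.

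**It may be late.** SAP 7.3 reports a stratification error in the past tense, so randomization had begun. This limits who benefits but does not remove the gap.

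**Conclusion.** The point holds as a gap in data collection. Protocol 5.5.2, 5.5.3 and footnote 2 of Table 1-2 send stopping drug and leaving the study down one path, and no section keeps a patient who stops early on the visit schedule. Followed as written, examination-based safety data and observed grades end at Early Termination. The Day 28 grade is then missing in the MMRM and carried forward in the ANCOVA, unless that visit falls within Day 25 to 31.

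The loss per patient follows from the schedule: three of four on-site visits for a Day 10 stopper. The trial-level effect does not, because no stopping rate is given. With an assumed one to five patients lost per arm, t-test power falls from 90.4% to between 89.2% and 82.8%. A reader might infer that the MMRM is biased towards the active arms by the d × 0.66 figures. The documents establish neither that size nor that direction; those figures rest wholly on the three assumptions in the working. The matter should be corrected, but it does not invalidate the trial.

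**What to change.** **Protocol (data collection only; reasons for stopping drug are untouched).** In 5.5.2, 5.5.3 and Table 1-2 footnote 2, separate discontinuation of study drug from withdrawal from the study. For drug discontinuation, record date and reason, collect the kit, and keep willing patients in the remaining scheduled assessments to Day 84, with the Day 28 grade and photograph as priority. Reserve Early Termination procedures for withdrawal from the study.

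**SAP, before database lock.** Report the two events separately in 6.2. State how off-drug Day 28 grades and Early Termination grades enter the mITT analyses, including the window that assigns an Early Termination grade to a visit and whether LOCF will be applied.

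**Cost.** A short amendment and a SAP clarification. The visits are already in the schedule, but the patients concerned bear the attendance. If off-drug grades are analysed as randomized, the estimate answers a treatment-policy question, may be smaller, and has somewhat lower power (column B). The amendment helps only patients still in follow-up; the SAP clarification is useful regardless.
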